6 CHANGES FROM THE CLINICAL TRIAL PROTOCOL

Changes to the planned analyses and the timing of these are summarised in Table 3.

Table 3 Changes in the planned statistical analyses

| Change category | Timing of change | Description of change | Reason for change |
|--|------------------|--|---|
| Change in the SAP compared to the protocol | Prior to DBL | Added frequency tables for safety laboratory interpretations. | To provide a better overview of the safety laboratory data. |
| | | Added the metabolites (SAD and MAD) for the PK endpoints in Table 1. | Included in analysis. |

7 CLINICAL DATABASE PROCESSING

7.1 General information

The clinical database is processed and generated according to The Clinical Data Interchange Standards Consortium (CDISC). CDISC is a Standard Developing Organization which develops and publishes standards to normalise the structure of clinical trial data and thereby simplify submissions to and reviews by authorities such as the Food and Drug Administration (FDA).

The CDISC standards for clinical studies are the Trial Data Tabulation Model (SDTM) and the Analysis Data Model (ADaM). The trial data will be structured into a database model reflecting the SDTM and will be compliant to SDTM Implementation Guide (SDTM-IG) version 3.3. The data used for statistical analysis will be structured to reflect the ADaM and be compliant to ADaM Implementation Guide (ADaM-IG) version 1.3.

Data values are collected according to, or mapped into, controlled terminology codelists defined by CDISC, whenever possible. The codelists are updated quarterly at [REDACTED] and the latest version available at trial start will be used. As per default, controlled terminology codelists will be used in all tables, listings, and figures. Custom codelists for test or parameter names will be used if applicable upon Sponsor's request, to align with protocol texts, or to adhere to other standard naming conventions (e.g., PK parameter name "Tmax" will be used instead of the CDISC term "Time of CMAX"). These custom codelists will be mapped in the "Parameter Name" field in the ADaM structure, while the CT will be kept in the SDTM predecessor fields to provide traceability back to CDISC codelists.

7.1.1 CDISC Compliance

The trial database will be CDISC compliant which means that the clinical database will be processed and generated according to CDISC standard. The database will be validated against SDTM and ADaM Validation rules using Pinnacle 21.

The following CDISC documentation will be generated:

- SDTM Data Definition Specification (also referred to as a Define -XML)
 - Define-XML transmits metadata that describes any tabular dataset structure and supports the interchange of dataset metadata for clinical research applications in a machine-readable format.
- ADaM Data Definition Specification (also referred to as a Define -XML)
 - Define-XML transmits metadata that describes any tabular dataset structure and supports the interchange of dataset metadata for clinical research applications in a machine-readable format.
- Annotated Electronic Case Report Form (eCRF)
 - Links the data collection fields used to capture trial data to the corresponding variables in the trial database. It enables the user to understand how the trial data were collected and to trace back from trial analysis results to the origin where it was collected.
- SDTM Reviewers' Guide
 - Intended to provide additional context and act as a single point of orientation for the SDTM datasets.
- ADaM Reviewers' Guide
 - Provides regulatory agency reviewers an orientation to the submitted analysis data in a consistent way and usable format.

7.2 Database modeling of trial design

The trial design is mapped to a SDTM trial design model containing the following structural components:

EPOCH: An interval of time in the planned conduct of a trial. An epoch is associated with a purpose (e.g., screening, randomisation, treatment, follow-up), and applies across all arms of the trial. Trial epochs follow a controlled terminology to represent the different trial parts (e.g., SCREENING, TREATMENT [X], FOLLOW-UP)

ELEMENT: Building blocks used to build up the entire trial length for all subjects. Information on ELEMENTs is extracted from the trial design and schedule of events in the protocol. ELEMENTs are defined to span the entire trial without gaps. One EPOCH may contain one or several ELEMENTs. All ELEMENTs must have transition rules in accordance with the protocol to determine start and end.

ARM: Subjects are allocated to trial arms depending on the trial design, either by randomisation or other allocation processes defined in the trial protocol. ARMs are defined as the total number of planned ways a subject can go through the trial (unique combination of trial ELEMENTs). All ARMs must contain a unique sequence of ELEMENTs.

VISIT: Trial visits are defined as planned timepoints during the trial where trial data is collected. A visit can be performed in clinic, by off-site contact with trial personnel (phone call, video conference or similar), or by subject initiated recordings of data. The visit schedule is extracted from protocol and eCRF design.

A schematic representation of the SDTM trial design is presented in Figure 1 to Figure 3.

Figure 1 Schematic representation of the SDTM trial design - SAD

[figure not shown]
[figure not shown]
[figure not shown]

Figure 2 Schematic representation of the SDTM trial design – SAD sub-study: food interaction**Figure 3 Schematic representation of the SDTM trial design - MAD**

*L = level. Dose levels for MAD cohorts are tentative at the time of producing this figure.

b.i.d.=two times a day (bis in die)

8 STATISTICAL DELIVERABLES

The following items will be delivered:

- Statistical analyses, summary tables, listings and figures as described under Sections 10-11.
- Clinical trial database delivered as a SAS-export file (SDTM and ADaM) and Excel files (ADaM)
- Define -XML for SDTM
- Define -XML for ADaM
- Annotated eCRF
- SDTM Reviewer's Guide
- ADaM Reviewer's Guide

9 STATISTICAL METHODOLOGY

In general, data will be presented in tables with the number of observations, arithmetic mean, standard deviation (SD), median, minimum and maximum value for continuous data. In addition, 95% confidence intervals (CIs) will be added for ECG, vital signs and safety laboratory data. Categorical data will be presented with counts and percentages. All collected data will be listed by subject and treatment, except for data pertaining to the exploratory endpoints, MIST analysis and urine metabolite profile, which will be reported elsewhere. Data is generally presented by part, treatment (active/placebo, or for the SAD sub-study, fasted/fed conditions), and dose group.

SAD and MAD data will be presented separately. Additionally, the tables and figures for the food interaction sub-study will be presented separated from those of the other SAD dose groups. The data for subjects receiving placebo will be presented pooled across groups, for SAD and MAD respectively.

Details on statistical analyses and descriptive summaries are specified below.

All statistical analyses and descriptive summaries will be performed using SAS version 9.4 (SAS institute, Cary, NC).

PK parameters will be calculated by Non-Compartmental Analysis (NCA) using the software Phoenix WinNonlin[®] version 8.3(Certara, U.S.A).

9.1 Analysis of the primary endpoints

9.1.1 Adverse Events (AEs)

AEs and SAEs will be recorded from the time when informed consent is obtained until the Follow-up Visit. AEs that occur before first treatment with IMP (baseline symptoms) will be listed separately.

All AEs will be described in terms of the treatment at which they occurred. AEs will be summarised by System Organ Class (SOC) and Preferred Term (PT) using the Medical Dictionary for Regulatory Activities (MedDRA) vocabulary. The number of subjects reporting AEs, and the number of AEs reported will be presented. The events will be tabulated by SOC, PT and by severity and relationship to IMP. SAEs will be presented in the same tabulations.

9.1.2 Physical examinations

Normal and abnormal findings will be specified and summarised by part, treatment, and dose group.

9.1.3 Columbia-Suicide Severity Rating Scale (C-SSRS)

This rating scale will be administered for screening of suicidal ideation and behaviour throughout the trial. No formal statistical analysis of the outcome will be performed, i.e., the data will be listed only. Any abnormal findings will be listed and treated as AEs or SAEs.

9.1.4 Electrocardiogram (ECG)

All continuous ECG data will be listed for each subject and summarised by part, treatment and dose group. In addition, ECGs will be categorised as "normal", "abnormal, not clinically

significant”, or ”abnormal, clinically significant” (as judged by the Investigator) and summarised by part, treatment and dose group.

9.1.5 *Telemetry (SAD only)*

Telemetry interpretations will be summarised in a frequency table, by treatment and dose group.

9.1.6 *Vital signs*

Vital signs (blood pressure, heart rate, respiratory rate and body temperature) will be summarised by part, treatment and dose group.

9.1.7 *Safety laboratory analyses*

Safety laboratory data will be summarised by part, treatment and dose group. Safety laboratory interpretations will be summarised by part, treatment and dose groups using frequency tables.

9.2 *Analysis of secondary endpoints*

9.2.1 *Pharmacokinetic analysis*

The following non-compartmental plasma PK parameters will be determined/calculated during the trial conduct:

SAD

Plasma IRL757

- T_{max} – Time to reach C_{max}
- C_{max} – The maximum observed plasma concentration
- AUC_{0-last} – Area under the plasma concentration versus time curve (AUC) from timepoint 0 to t, where t represents the timepoint of the last detectable plasma concentration
- AUC_{0-24h} – (AUC) from timepoint 0 to 24 h
- AUC_{0-inf} – AUC from timepoint 0 extrapolated to infinity
- CL/F – Apparent clearance
- V_z/F – Apparent volume of distribution associated with terminal phase
- λ_{z} – Eliminate rate constant associated with the terminal phase
- $T_{1/2}$ – Terminal plasma elimination half-life

For the 3 main metabolites following PK parameters will be determined/calculated (if possible):

- T_{max}
- C_{max}
- AUC_{0-last}
- AUC_{0-24h}
- AUC_{0-inf}
- λ_{z}
- $T_{1/2}$

Parameters that are only presented in listings

- Lambda_z lower – Lower limit on time for values to be included in the calculation of Lambda_z
- Lambda_z upper – Upper limit on time for values to be included in the calculation of Lambda_z
- No points lambda_z – Number of points used in computing lambda_z
- Span – The ratio between the interval used for determination of lambda_z and the terminal $T_{1/2}$
- $\text{Rs}_q \text{ adj}$ – Goodness of fit statistic for the terminal phase, adjusted for the number of points used in the estimation of lambda_z .
- T_{last} – Time of last observed plasma concentration
- $\text{AUC}_{\text{extr}\%}$ – Percentage of $\text{AUC}_{0-\text{inf}}$ due to extrapolation from T_{last} to infinity
- $\text{AUC}_{0-48\text{h}}$ – (AUC) from timepoint 0 to 48 h

Relative bioavailability

- $F_{\text{rel}} \text{ AUC}_{0-\text{last}}$ – Relative bioavailability for $\text{AUC}_{0-\text{last}}$ after fed and fasting conditions
- $F_{\text{rel}} \text{ AUC}_{0-\text{inf}}$ – Relative bioavailability for $\text{AUC}_{0-\text{inf}}$ after fed and fasting conditions
- $F_{\text{rel}} C_{\text{max}}$ – Relative bioavailability for C_{max} after fed and fasting conditions

Fasted value will be used in the denominator.

MAD

After first dose IRL757:

- T_{max}
- C_{max}
- $\text{AUC}_{0-\text{tau}}$ – AUC from timepoint 0 to end of dosing interval (12 hour)
- Lambda_z
- $T_{1/2}$

For the 3 main metabolites following PK parameters will be determined/calculated (if possible):

- T_{max}
- C_{max}
- $\text{AUC}_{0-\text{tau}}$
- Lambda_z
- $T_{1/2}$

After last dose (at steady state (if reached)) IRL757:

- T_{max}
- C_{max}
- C_{avg} - Average concentration over dosing interval
- C_{min} - Minimum observed concentration at the end of the dosing interval
- $\text{AUC}_{0-\text{tau}}$ – AUC during dosing interval (12 hour) at steady state

- CL/F – Apparent clearance at steady state
- V_z/F – Apparent volume of distribution at steady state
- λ_z
- $T_{1/2}$

For the 3 main metabolites following PK parameters will be determined/calculated (if possible):

- T_{max}
- C_{max}
- $AUC_{0-\tau}$
- λ_z
- $T_{1/2}$

Other:

- $AR C_{max}$ – Accumulation ratio of C_{max} , ratio of last dose day over first dose day
- $AR AUC_{0-\tau}$ – Accumulation ratio of $AUC_{0-\tau}$, ratio of last dose day over first dose day

Parameters that only are presented in listings

- λ_z lower
- λ_z upper
- No points λ_z
- Span
- Rsq_{adj}
- T_{last}
- $AUC_{extr\%}$

The following non-compartmental urine PK parameters will be calculated during the trial conduct:

SAD

- A_e – Amount IRL757 excreted unchanged (IRL757 and major metabolites)
- F_e – Fraction of dose excreted in urine (only IRL757)
- CL_{renal} – Renal clearance (only IRL757)

MAD

- A_e – Amount IRL757 excreted unchanged (IRL757 and major metabolites)
- F_e – Fraction of dose excreted in urine (IRL757) for the last dose interval (only IRL757)
- CL_{renal} – Renal clearance (only IRL757)

Following units will be used:

- Time: h
- Concentration: umol/L
- AUCs: h*umol/L
- Extrapolated AUC and Fe: %
- λ_{dz} : /h
- Apparent Clearance: L/h
- Apparent Volume of distribution: L
- A_e : umol and/or mg

Non-compartmental analysis will be based on the actual sampling times recorded during the trial. For the purpose of calculating PK parameters, concentrations below lower limit of quantification (LLOQ) occurring before C_{max} will be treated as zero. Concentrations below LLOQ occurring after C_{max} will be omitted from the analysis.

T_{max} , T_{last} , and C_{max} will be based on the observed plasma concentration data.

All AUC will be assessed by integration of the plasma concentration vs time curve using linear interpolation for increasing plasma levels and logarithmic interpolation for decreasing plasma levels (Linear Up-Log Down method).

AUC_{0-last} will be calculated from time 0 to the time t of the last detectable plasma concentration.

For AUC_{0-inf} the area will be calculated to the last timepoint showing a measurable plasma concentration and then extrapolated to infinity using the concentration in the last quantifiable sample and λ_{dz} .

$$AUC_{0-inf} = AUC_{0-last} + \frac{C_{last}}{\lambda_{dz}}$$

Partial AUC/ AUC_{tau} will be derived according to specified time windows/dosing interval, if the end time of the interval does not occur at an actual timepoint either linear interpolation or extrapolation will be used for derivation of the partial AUC. Extrapolation, using λ_{dz} , will only be used if the end time of specified interval occur after last detectable plasma concentration.

Formulas for calculation of AUC

- Linear trapezoidal rule:

$$AUC|_{t_1}^{t_2} = \delta t \times \frac{C_1 + C_2}{2}$$

- Logarithmic trapezoidal rule:

$$AUC|_{t_1}^{t_2} = \delta t \times \frac{C_2 - C_1}{\ln\left(\frac{C_2}{C_1}\right)}$$

where t = time, c = concentration, $\delta t = t_2 - t_1$.

Formulas for interpolation (to find C^* at time t^* for $t_1 < t^* < t_2$)

- Linear interpolation rule:

$$C^* = C_1 + \left| \frac{t^* - t_1}{t_2 - t_1} \right| (C_2 - C_1)$$

- Logarithmic interpolation rule:

$$C^* = \exp \left(\ln(C_1) + \left| \frac{t^* - t_1}{t_2 - t_1} \right| * (\ln(C_2) - \ln(C_1)) \right)$$

where t = time, c = concentration

λ_{z} , the first order rate constant associated with the terminal portion of the curve will be determined by lin-logarithmic regression of the terminal elimination phase of individual plasma concentration vs time curves. Determination of λ_{z} requires identification of a sufficiently linear terminal phase (as determined by visual inspection of the lin-log plasma concentration vs time plot with the regression line) consisting of at least 3 terminal concentration values (not including C_{\max}). If this is not achieved, λ_{z} and its dependent PK parameters will not be reported for that profile.

In the following cases, λ_{z} dependent PK parameters will be flagged in listings as potentially unreliable:

- λ_{z} estimation is based on a period of less than 1.5 times the resulting $T_{1/2}$.
- The Rsq adjusted value of the regression line is < 0.85 .
- The estimated % extrapolated AUC is $> 20\%$ $((AUC_{0-\text{inf}} - AUC_{0-\text{last}} / AUC_{0-\text{inf}}) * 100)$.

$T_{1/2}$ will be calculated accordingly:

$$T_{1/2} = \frac{\ln(2)}{\lambda_{z}}$$

Span will be calculated accordingly:

$$\text{Span} = \frac{\lambda_{z \text{ upper}} - \lambda_{z \text{ lower}}}{T_{1/2}}$$

CL will be calculated accordingly:

$$\text{Single dose: } \frac{CL}{F} = \frac{Dose}{AUC_{0-inf}} \quad \text{Steady state: } \frac{CL}{F} = \frac{Dose}{AUC_{0-tau}}$$

V_z will be calculated accordingly:

$$\text{Single dose: } \frac{V_z}{F} = \frac{Dose}{\lambda_{dz} * AUC_{0-inf}} \quad \text{Steady state: } \frac{V_z}{F} = \frac{Dose}{\lambda_{dz} * AUC_{0-tau}}$$

A_e will be calculated accordingly:

$$A_e = \sum_{i=1}^n v_i * c_i$$

Let v be the volume of urine and c the concentration of drug in urine, the product of v and c for one interval (i) represent A_e . The A_e over 0-12 hours (MAD BID), 0-24 hours (SAD 1-4) and 0-48 hours (SAD 5) is the sum of all intervals. The weight of the collected urine fractions will be calculated assuming a urine density of 1.00 g/mL.

CL_{renal} will be calculated accordingly:

$$\text{Single dose: } CL_{renal} = \frac{A_e}{AUC_{0-end of dosing interval}}$$

$$\text{Steady state: } CL_{renal} = \frac{A_e}{AUC_{0-tau}}$$

If there is a confirmed dosing error during the trial, the pharmacokinetic data for that period will only be included in the listings but excluded from descriptive and statistical analyses. In case of missed blood samples, potential impact on PK parameters will be assessed for each individual case. PK parameters with a high degree of uncertainty due to missing samples (e.g., multiple samples missing around C_{max}) will be flagged as unreliable in the report and may in rare cases be excluded from summary tables, descriptive statistics, and statistical analysis.

Descriptive statistics for the PK parameters will be presented by part and dose group using summary statistics with the number of measurements (n), arithmetic mean, SD, as well as median, minimum and maximum values. For all applicable PK parameters, the geometric mean and geometric coefficient of variation (CV%) will be presented. For the parameter T_{max} , the number of observations, and median, minimum and maximum values will be presented only. For the relative bioavailability ratios, 90% confidence intervals (CIs) are presented.

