Eligible subjects will be confined to the research clinic from the evening before each dosing (Day -1) until 48 hours post-dose (Day 3). The subjects should be fasting overnight (10 hours) before dose administration on Day 1. During the in-clinic period, PK blood sampling and urine sampling will be performed, from IMP administration until 48 hours post-dose and until 24 hours post-dose respectively.

A Follow-up Visit will be performed 5-10 days after administration of Investigational Medicinal Product (IMP).

The food interaction sub-study will include six (6) additional subjects. The six subjects will be administered IRL757 in fasted and fed conditions. A standardized breakfast meal will be consumed within 30 minutes prior to IMP administration, in order to study potential food interactions. After the completion of cohort 4, safety and PK data will be evaluated to determine which dose level will be used for the food interaction sub-study. For each administration, the subjects will be confined to the research clinic from the evening before dosing (Day -1) until at least 48 hours after administration (Day 3).

In the MAD part of the trial, 24 or 36 eligible and consenting subjects will be allocated to one of two (2) or three (3) cohorts; IRL757 Dose Level 1, IRL757 Dose Level 2, and IRL757 Dose Level 3 if applicable, with 12 subjects in each cohort. Within each cohort subjects will be randomly assigned to treatment with placebo or IRL757; three (3) subjects will be given placebo, and nine (9) subjects will be given IRL757.

The 12 subjects in a cohort will be divided into four (4) groups; a sentinel group, two (2) groups of three (3) subjects each and one (1) group of four (4) subjects. In each cohort, the “sentinel group” of two (2) subjects (one [1] active drug/ one [1] placebo) will be dosed first and closely observed for 24 hours before starting the dosing in the following group. Subsequent groups in the cohort will be dosed approximately 24 hours apart. In each group the subjects will be dosed with an interval of at least 30 minutes between subjects. It is foreseen that subjects will be treated with two (2) daily oral doses of IRL757 or placebo administered at the same time during ten (10) consecutive days (the dosing interval is subject to change and will be confirmed depending on the results from the SAD part of the trial).

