There will be an interval of at least one (1) week between last administration in a cohort and initiation of next cohort to allow time for PK and safety data to be analysed, evaluated and reviewed by the iSRC. The iSRC will have the choice to recommend to escalate the dose as planned, reduce or increase the dose escalation step, repeat the dose, reduce the dose or terminate the trial.

The decision on dose levels will be done following the SAD part of the trial and a cautious selection of dose will be done if dosing is expected to approach the exposure limit.

Screening (Visit 1) will take place between Day -28 and Day -1.

Eligible subjects will be confined to the research clinic from the evening before first dosing (Day -1) until Day 11 and will come back to the clinic on Day 12 for extended PK and safety samples (including 48 hours post the last morning dose). The subjects should be fasting overnight (10 hours) before dose administration on Day 1 and Day 10. A Follow-up Visit will be performed 5-10 days after last administration of IMP.

An additional third cohort (IRL757 Dose Level 3), with twelve (12) additional subjects may be implemented following the review of data of the SAD part of the trial. The cohorts are described in Table 2.

Table 2 MAD dosing groups

Cohort	Dose	Groups	
Cohort 1 (n=12)	Dose Level 1	2 + 3 + 3 + 4	Sentinel group (n=2): 1 active, 1 placebo Subsequent groups (n=3+3+4): 8 active, 2 placebo
Cohort 2 (n=12)	Dose Level 2	2 + 3 + 3 + 4	
Cohort 3 (n=12)	Dose Level 3	2 + 3 + 3 + 4	

Investigational Medicinal Products (IMP), dosage and mode of administration

IRL757 half-life is expected to be 2-7 hours.

IRL757 capsules [REDACTED]

Placebo capsules: [REDACTED]

Duration of treatment

Subjects included in the SAD part will be treated with one (1) single oral dose of IRL757 or placebo (see Table 1).

Subjects included in the food interaction sub-study will be treated with two (2) oral doses of IRL757.

Subjects included in the MAD part will receive two (2) daily oral doses of IRL757 or placebo for ten (10) consecutive days. The number of daily doses in the MAD part of the trial will be confirmed following review of PK data from the SAD part of the trial.

Duration of each subject's involvement in the trial

Subjects will be screened for eligibility according to trial-specific inclusion/exclusion criteria at Visit 1 (Screening visit) within four (4) weeks prior to start of IMP administration.

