5.7 Handling of dropouts, missing data and outliers

Outliers will be included in summary tables and listings and will not be handled separately in any analyses. All collected data, even if not tabulated, will be listed. Generally, no imputation of data will be performed. However, when calculating statistics for PK plasma concentrations, concentrations under LLOQ will be replaced with LLOQ/2 if more than 50% of the values for a given time point are above LLOQ. For figures presenting individual PK concentrations, no imputation is performed for values under LLOQ. For imputation of PK plasma concentration below LLOQ with the purpose of calculating PK parameters, see Section 9.2.1.

Safety laboratory concentrations under LLOQ will be replaced with LLOQ/2 and concentrations over ULOQ will be replaced with ULOQ for the purpose of calculating descriptive statistics.

In case of missing start and stop times of AEs that cannot be investigated further, missing data will be imputed according to a worst-case scenario, i.e., start time will be imputed as the closest time point post first intake of IMP and end time as 23:59, resulting in the longest possible treatment emergent duration of the AE.

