| | n | xx | xx | xx |
| | Mean (SD) | x.xx (x.xx) | x.xx (x.xx) | x.xx (x.xx) |
| | Median (Min, Max) | x.xx (x.x, x.x) | x.xx (x.x, x.x) | x.xx (x.x, x.x) |
| | | Geometric Mean (geo CV%) | x.xxx (x.x%) | x.xxx (x.x%) |

Data based on [population]. n: Number of observations. SD: Standard deviation. CV%: Coefficient of variation described as percentage. Geo CV%: Geometric coefficient of variation described as percentage calculated using log-transformed standard deviation. NC: Not calculated - number of evaluable observations less than 3 or more than half of the observations are BLQ. NA: Not available - no evaluable observations. SAS program: [PROGRAM NAME].sas.

Dataset version: ADXX YYYY-MM-DDTHH:MM:SS. Run by: [USERNAME] YYYY-MM-DDTHH:MM:SS. EDC data extracted: YYYY-MM-DDTHH:MM:SS.

Table PP 3 Urinary excretion of IRL757 after last dose - MAD (Pharmacokinetic analysis set)

| | | | Parameter (unit) | | |
|---|--------------------------|--------------------------|-----------------------------|-----------------|-----------------------------|
| Cohort | Assessment time interval | | IRL757 concentration (unit) | Volume (unit) | Ae per time interval (unit) |
| IRL757 XX mg, YY umol b.i.d. (N=9) | 0-8 h | n/BLQ | xx/xx | xx/xx | xx/xx |
| | | Mean (SD) | x.xx (x.xx) | x.xx (x.xx) | x.xx (x.xx) |
| | | Median (Min, Max) | x.xx (x.x, x.x) | x.xx (x.x, x.x) | x.xx (x.x, x.x) |
| | | Geometric Mean (geo CV%) | x.xxx (x.x%) | x.xxx (x.x%) | x.xxx (x.x%) |
| | 8-12 h | n/BLQ | xx/xx | xx/xx | xx/xx |
| | | Mean (SD) | x.xx (x.xx) | x.xx (x.xx) | x.xx (x.xx) |

| Cohort | Assessment time interval | Parameter (unit) | | | |
|---|--------------------------|-----------------------------|-----------------|-----------------------------|-----------------|
| | | IRL757 concentration (unit) | Volume (unit) | Ae per time interval (unit) | |
| IRL757 XX mg, YY umol b.i.d. (N=9) | 12-24 h | Median (Min, Max) | x.xx (x.x, x.x) | x.xx (x.x, x.x) | x.xx (x.x, x.x) |
| | | Geometric Mean (geo CV%) | x.xxx (x.x%) | x.xxx (x.x%) | x.xxx (x.x%) |
| | | n/BLQ | xx/xx | xx/xx | xx/xx |
| | | Mean (SD) | x.xx (x.xx) | x.xx (x.xx) | x.xx (x.xx) |
| | 0-8 h | Median (Min, Max) | x.xx (x.x, x.x) | x.xx (x.x, x.x) | x.xx (x.x, x.x) |
| | | Geometric Mean (geo CV%) | x.xxx (x.x%) | x.xxx (x.x%) | x.xxx (x.x%) |
| | | n/BLQ | xx/xx | xx/xx | xx/xx |
| | | Mean (SD) | x.xx (x.xx) | x.xx (x.xx) | x.xx (x.xx) |

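### SAP 9.2.1 gives no rule for the steady-state Cmin when the Day 10 12 h sample is below LLOQ; if such samples occur, omitting them pushes the Cmin summary up

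*SAP*

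**What the plan says.** SAP 9.2.1 has two BLQ rules for deriving PK parameters. Before the peak, "concentrations below lower limit of quantification (LLOQ) occurring before C_{max} will be treated as zero". After it, "Concentrations below LLOQ occurring after C_{max} will be omitted from the analysis".

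The same section lists Cmin among the MAD parameters after the last dose and defines it as "Minimum observed concentration at the end of the dosing interval", with an interval of 12 hours.

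SAP 5.7 has a different rule for summarising plasma concentrations: "concentrations under LLOQ will be replaced with LLOQ/2 if more than 50% of the values for a given time point are above LLOQ". It then limits its own reach: "For imputation of PK plasma concentration below LLOQ with the purpose of calculating PK parameters, see Section 9.2.1".

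Table PC 1 (MAD) summarises concentrations by time point with an n/BLQ row. Table PP 2 (MAD) summarises Cmin with n, mean, median and geometric mean, but no BLQ count. Both tables carry the footnote "NC: Not calculated - number of evaluable observations less than 3 or more than half of the observations are BLQ".

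In each MAD cohort, "three (3) subjects will be given placebo, and nine (9) subjects will be given IRL757" (Protocol synopsis). Day 10 has a morning dose only, with samples pre-dose and at 10, 12 and 14 h among others (Protocol Table 7, footnotes 8 and 9). The Protocol also states: "IRL757 half-life is expected to be 2-7 hours".

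**The concern.** Omitting late BLQ values is a usual choice for AUC and lambda_z. A minimum is different, because the omitted value is the one the parameter is meant to capture. A BLQ sample at 12 h on Day 10 comes after Cmax, so the parameter rule removes it, and the LLOQ/2 rule in 5.7 does not bring it back. The SAP foresees an interval that outlasts the last detectable concentration for AUC0-tau, which is then extrapolated with lambda_z. It has no counterpart for Cmin.

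Whether a subject is lost would then depend on how low that subject's trough is. The remaining Cmin values would describe only subjects with quantifiable troughs. The report could also show two different 12 h troughs for one dose group, from the same samples: one in Table PC 1 with LLOQ/2, the other in Table PP 2 without the BLQ subjects.

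**Working it through.** The documents give no bias, precision or power figure for Cmin, so there is nothing of the plan's own to reproduce.

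**Inputs from the documents.** Active subjects per MAD cohort: 12 × 3/4 = 9. Dosing interval 12 h. Half-life 2-7 h. LLOQ: a template placeholder. Doses: not available.

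**When a biased summary can appear.** The NC footnote withholds the result when more than half are BLQ, that is 5 or more of 9. The LLOQ/2 rule in 5.7 needs more than 50% above LLOQ, that is at least 5 of 9. So 1 to 4 BLQ troughs of 9 give a reported value in both tables.

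**How low the trough is.** Assuming one compartment and instant absorption, C12/Cmax = 2^(-12/half-life):
- 2 h: 2^(-6) = 1.6%
- 3 h: 2^(-4) = 6%
- 4 h: 2^(-3) = 12.5%
- 7 h: 2^(-1.71) = 30%

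If LLOQ is below about 1.6% of Cmax, no trough is expected to be BLQ anywhere in the stated range.

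**Worked example.** Nine subjects, equal Cmax, half-lives spread evenly from 2 to 7 h. The true geometric mean (GM) of C12/Cmax is 0.1153 and the true arithmetic mean is 0.1576.

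| LLOQ/Cmax | BLQ | GM, omitted | GM, LLOQ/2 | GM, 10 h value used | Arithmetic mean, BLQ as zero |
|---|---|---|---|---|---|
| 0.5% | 0 | 0.1153 (1.00×) | 0.1153 | 0.1153 | 0.1576 |
| 2% | 1 | 0.1480 (1.28×) | 0.1097 | 0.1245 (n = 9) | 0.1558 |
| 5% | 2 | 0.1771 (1.54×) | 0.1146 | 0.1581 (n = 8) | 0.1512 |

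In the 5% row, Table PP 2 would show 0.1771 and Table PC 1 0.1146 for the same samples. The 10 h column there has n = 8 because the 2 h subject's 10 h value, 2^(-5) = 3.1% of Cmax, is itself BLQ.

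**Nine lognormal troughs, the lowest k BLQ.** The trough CV is an assumption. Error in the GM:

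| BLQ | Omitted, CV 30 / 60 / 100% | LLOQ/2, CV 30 / 60 / 100% |
|---|---|---|
| 1 of 9 | +6 / +11 / +17% | -7 / -6 / -5% |
| 2 of 9 | +11 / +21 / +33% | -12 / -9 / -7% |
| 4 of 9 | +21 / +44 / +72% | -20 / -13 / -6% |

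**Steady-state simulation.** Assumptions: one compartment, ka 2.5/h, 12 h interval, median half-life 2, 4 or 7 h, elimination-rate CV 20, 30 or 40%, volume CV 25%. LLOQ is set so that on average 1, 2 or 3 of 9 troughs are BLQ. That makes 3 × 3 × 3 = 27 scenarios of 40,000 replicates each, keeping replicates with at least 5 quantifiable troughs.

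| Half-life | Rise in GM, omitted | Cmax/LLOQ at which this occurs |
|---|---|---|
| 2 h | 22% to 134% | about 60 to 460 |
| 4 h | 12% to 62% | about 8 to 24 |
| 7 h | 9% to 41% | about 3 to 7 |

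Rises above about 62% occur only at the 2 h half-life. The 134% needs a trough geometric CV near 460%. In the same 27 scenarios the arithmetic mean rises 7% to 37%. LLOQ/2 gives -11% to +26% in the GM and is closer to the truth than omission in all 27.

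**Other ways to fill the gap.**
- Using the 10 h value inflates an affected subject's Cmin by 2^(2/half-life) = 2.00, 1.41 and 1.22 times at 2, 4 and 7 h. The group GM rises about 3-37%, taking every 10 h value as available. Where the 10 h value is also BLQ and omitted, the rise lies between that and full omission.
- Using a BLQ pre-dose value set to zero lowers the arithmetic mean (last column of the worked example), and the geometric mean cannot be computed.

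**The case against.** The strongest reply is that nothing here is shown to happen. Without LLOQ and doses, nobody can say that any Day 10 trough will be BLQ, and the simulation chooses LLOQ so that some are. That stands. BLQ troughs at 7 h need Cmax only 3 to 7 times LLOQ and are unlikely. At 4 h the ratio is still only about 8 to 24. Near 2 h the trough is about 1.6% of Cmax, so even a doubling is small in absolute terms.

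A reader might infer that subjects will drop out and that Cmin will be biased upward. The documents do not support that as a prediction. The SAP does not say what Cmin becomes once the 12 h value is omitted. Its end-of-interval definition points to a missing Cmin, but it does not rule out the 10 h value (upward, possibly with nobody lost) or a zeroed pre-dose value (downward).

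A reader might also infer that comparisons between doses are distorted. No test on Cmin between doses is planned: dose proportionality and accumulation use AUC0-tau and Cmax. Cmin is not among the MAD endpoints in the Protocol synopsis or in SAP Table 1.

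Nor would the loss be hidden. Table PP 2 prints n under a header of N=9, Table PC 1 gives the same trough with its BLQ count, and the listings show every subject.

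What remains is that the stated omission rule covers Cmin, leaves it undefined in a foreseeable case, and conflicts with the convention used for the same sample elsewhere in the SAP.

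**Conclusion.** The point holds as a conditional gap of minor weight. If 1 to 4 of 9 Day 10 12 h samples are BLQ, the SAP's definition and omission rule together leave those subjects without a Cmin, and the reported summary is too high. With 1 to 3 of 9 BLQ on average, the rise in the geometric mean is roughly 10-60% in most scenarios. This rests on the one-compartment model and the assumed CVs and LLOQ. The figures above that range should not be read as expected, since they need extremely variable troughs at the shortest half-life. With no BLQ trough the effect is zero. The consequence is confined to a descriptive parameter and to its agreement with Table PC 1; no endpoint or planned test depends on it.

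**What to change.** Add to SAP 9.2.1:

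> Cmin is taken from the 12 h sample on Day 10, not from the pre-dose or 10 h sample. The omission of post-Cmax values below LLOQ does not apply to Cmin. If the 12 h sample is below LLOQ, Cmin is set to LLOQ/2 for descriptive statistics, as in Section 5.7, and is listed as BLQ.

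Show n/BLQ for Cmin in Table PP 2 and keep the existing NC rule. Leave the omission rule as it is for AUC and lambda_z.

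The cost is a short addition to the SAP text and one changed table row, with no new data, samples or subjects. LLOQ/2 is approximate and not unbiased. When troughs vary little it errs downward, and at a trough CV of 30% by about as much as omission errs upward. Its merit is that it keeps every subject in the summary and brings Table PP 2 into line with Table PC 1.
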